10.2. Populations for Analyses

For purposes of analysis, the following populations are defined:

Population	Description
Entered	All patients who give informed consent.
Enrolled	All patients who receive at least 1 dose of open-label Humalog in the 2-week lead-in period.
Randomized	All patients who are randomly assigned to study treatment at Visit 4 and receive at least 1 dose of the randomly assigned IP. Treatment will be defined on the basis of the treatment the patients are assigned to.

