TEAEs	Enrolled Population	Prior to first dose of open-label Humalog (or Visit 2 date if the dose date is missing)	The entire lead-in period after first dose of open-label Humalog and prior to first dose of IP (or Visit 4 date if the dose date is missing)
4-Week of Each Randomized Treatment Period While on IP (from first to last dose of IP in each 4-week randomized treatment period)			
Unplanned infusion set changes by reason (pump occlusion alarm; unexplained high BG; infusion site reaction (pain, redness or swelling at infusion site), or infusion set problem (infusion set kinked, pulled out, leaking, reservoir empty, etc.))	Randomized Population	From first to last dose of open-label Humalog, excluding data (if any) that are collected while patients temporarily are off pump or off open-label Humalog	From first to last dose of IP in each randomized treatment period (Period I and Period II), excluding data (if any) that are collected while patients temporarily are off pump or off IP

Baseline and Post-Baseline Definitions and Patient Population by Study Period and Type of Analysis

Study Period/Analysis	Patient Population	Baseline Observations	Post-Baseline Observations
Time interval until infusion set change	All patients in the Randomized Population with a baseline and a post-baseline observation	From first to last dose of open-label Humalog, excluding data (if any) that are collected while patients temporarily are off pump or off open-label Humalog	From first to last dose of IP in each randomized treatment period (Period I and Period II), excluding data (if any) that are collected while patients temporarily are off pump or off IP
Hypoglycemia events	Randomized Population	From first to last dose of open-label Humalog	Visits 4, 5, 6, 7, 8, 9 and 10 that fall between first and last dose of IP in each randomized treatment period (Period I and Period II). More detailed analysis period can be found in Section 6.10.4.
HbA1c summary statistics	All patients in the Randomized Population with a baseline and at least one post-baseline observation while on IP	Last value of Visits 1-4 prior to or on the date of the first dose of IP	Visits 7 and 10 while on IP ^d
1,5-AG	All patients in the Randomized Population with a baseline and at least one post-baseline observation while on IP	Visit 4 prior to or on the date of the first dose of IP	Visits 7 and 10 while on IP

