Pump factors - CR, ISF, and AIT ^b	All patients in the Randomized Population with a baseline and at least one post-baseline observation	Last value of Visits 2-4 prior to or on the date of the first dose of IP	Last observation 1 day prior to Visit 7 and last observation 1 day prior to Visit 10 prior to last dose in IP of each randomized treatment period (Period I and Period II) excluding data (if any) that are collected while patients temporarily are off pump or off IP

Baseline and Post-Baseline Definitions and Patient Population by Study Period and Type of Analysis

Study Period/Analysis	Patient Population	Baseline Observations	Post-Baseline Observations
4-Week of Each Randomized Treatment Period Regardless of IP use (from randomization to Week 4 of each randomized treatment period regardless of IP use)			
TEAEs	Randomized Population	Prior to first dose of randomized IP (or Visit 4 if the dose date is missing)	Each 4-week randomized treatment period regardless of IP use
Weight and vital signs	All patients in the Randomized Population with a baseline and a post-baseline observation	Last of Visits 2-4	Visits 7 and 10 regardless of IP use
Week 2-4 of Each Randomized Treatment Period while on IP			
CGM outcome variables	All patients in the Randomized Population (with a baseline and a post-baseline observation for continuous variables, unless otherwise specified ^c)	From first to last dose of open-label Humalog, excluding data (if any) that are collected while patients temporarily are off pump or off open-label Humalog	From first to last dose of IP in each randomized treatment period (Period I and Period II), excluding data (if any) that are collected while patients temporarily are off pump or off IP
Week 2-4 of Each Randomized Treatment Period Regardless of IP			
Basal, bolus, and total insulin doses, bolus/total insulin dose ratios ^d	All patients in the Randomized Population with a baseline and a post-baseline observation	Last of Visits 2-4	Visits 7 and 10 regardless of IP use
Basal, bolus, and total insulin doses, bolus/total insulin dose ratios by infusion set wear day, by meal, and by infusion set wear day and meal ^e	All patients in the Randomized Population with a baseline and a post-baseline observation	Last of Visits 2-4	Last observed value before/at Visit 7 and before/at Visit 10 regardless of IP use

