6.10.2. Adverse Events

Events that are newly reported after the first dose of rapid-acting insulin provided as study drug (ie, open-label Humalog used during the lead-in period or IP used during each of the two 4-week randomized treatment periods) or are reported to worsen in severity from baseline (defined in [Table ITSM.6.2](#) for each specific study period) will be considered treatment-emergent adverse events (TEAEs). Events that continue during more than 1 study period (lead-in, Period I, Period II) with the same severity will only be counted once for the first study period.

The MedDRA Lowest Level Term (LLT) will be used in the treatment-emergent assessment. The maximum severity for each LLT during the baseline period will be used as baseline severity. For events occurring on the day of first dose of blinded insulin provided in this study during each treatment period (lead-in, Period I and Period II), the CRF-collected flag will be used to determine whether the event started or worsened post-treatment, and/or the treatment of which period the AE should be assigned.

In an overview table, the number and percentage of patients who experienced a TEAE, experienced a serious adverse event (SAE), died due to an AE, and discontinued from study due to an AE will be summarized.

The number and percentage of patients with SAEs and who discontinued from the study due to an AE will be summarized using MedDRA PT nested within SOC if any such events occurred. Prescott's exact test will be performed for treatment comparison. The number and percentage of patients with TEAEs will be summarized by treatment using MedDRA PT nested within SOC. Events will be ordered by decreasing frequency within SOC. As an additional table, the percentages of patients with TEAEs will be summarized by treatment using MedDRA PT (without regard to SOC). Events will be ordered by decreasing frequency in total group. Statistical comparisons will be applied at both the SOC and PT levels. Prescott's exact test will be performed for treatment comparison.

The number and percentage of patients with TEAEs by maximum severity will be summarized by treatment using MedDRA PT nested within SOC. For each patient and TEAE on each treatment, the maximum severity for the MedDRA PT is the maximum postbaseline severity

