6.10.4.3. Infusion Site Reaction

The infusion site reactions will be searched by MedDRA PTs from all TEAEs. The number and percentage of patients experiencing at least one treatment-emergent infusion site reaction will be summarized and compared by treatment using Prescott's exact test.

For infusion site reactions identified by MedDRA PTs, the presence and severity of erythema, induration, pain, pruritus, and edema are collected on the eCRF and will be summarized for each treatment. There will be no statistical comparison between treatments.

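### A resolved lead-in reaction can stop later same-term reactions counting as treatment-emergent on either insulin; the infusion site and hypersensitivity comparisons need a supplementary new-onset analysis

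*SAP*

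**What the plan says.** SAP Table ITSM.6.2 (section 6.1) gives the TEAE baseline for the randomized periods as "Prior to first dose of randomized IP (or Visit 4 if the dose date is missing"), and the post-baseline window as "Each 4-week randomized treatment period regardless of IP use". The baseline has no lower bound, and the same one serves both periods and both insulins. It therefore contains the lead-in, when patients infuse open-label Humalog. The Enrolled population in Protocol 10.2 is defined by that exposure: "All patients who receive at least 1 dose of open-label Humalog in the 2-week lead-in period".

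SAP 6.10.2 supplies the rule for comparing with baseline: "The MedDRA Lowest Level Term (LLT) will be used in the treatment-emergent assessment", and then "The maximum severity for each LLT during the baseline period will be used as baseline severity". Nothing limits this to events still present at the first randomized dose. The one carry-over sentence in 6.10.2 concerns events that continue from one study period into the next at unchanged severity. It does not mention events that resolve and come back.

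The definition also has a limb that does not rest on severity: "Events that are newly reported after the first dose of rapid-acting insulin provided as study drug".

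The events of special interest are drawn from the TEAE set. SAP 6.10.4.3 states "The infusion site reactions will be searched by MedDRA PTs from all TEAEs", and 6.10.4.2 does the same for systemic hypersensitivity. Both are compared by Prescott's exact test. Lead-in TEAEs have their own overall summary, covering "The entire lead-in period after first dose of open-label Humalog and prior to first dose of IP".

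**The concern.** Infusion site reactions come and go. Sets are changed every 3 days, which is about 14/3 = 4.7 sets in the lead-in and 28/3 = 9.3 in each treatment period, and a reaction at a new site is clinically a new event. If one mild, resolved lead-in reaction fixes baseline severity at mild for that LLT, then no later mild reaction of that LLT counts on either insulin.

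Two things are at stake. First, the frequency of local and hypersensitivity reactions is understated on both products. Second, the filter is set during exposure to the comparator and before any exposure to the new formulation, so it need not act equally on the two. It could tilt the comparison, or it could mask a real excess on LY900014 by removing the most reactive patients from the count.

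**Working it through.** **Inputs.** From the documents: 2-week lead-in, 4-week periods, 42 randomized (21 per sequence), alpha 0.10 two-sided. The documents give no adverse event rate, so there is no stated figure to reproduce, and every rate below is an assumption.

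**Step 1: simple case.** If a reactive patient has same-LLT, same-severity events at Poisson rate r per 4 weeks, the chance of one in a 2-week lead-in is 1 − exp(−r/2). This is the share of such patients' period positives that is lost: 10% at r = 0.21, 22% at r = 0.5 and 39% at r = 1.

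**Step 2: variation between patients.** Let patient rates follow a gamma distribution with shape 0.3 and scale X per 4 weeks. True 4-week incidence is p = 1 − (1+X)^−0.3, so X = 1.104 for p = 20% and 0.421 for p = 10%. All reactions are treated as one LLT at one severity, which is the worst case for suppression.

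- Humalog counted = (1+X/2)^−0.3 − (1+3X/2)^−0.3. At 20%: 0.8765 − 0.7460 = 13.0%. At 10%: 0.9443 − 0.8635 = 8.1%.
- LY900014 counted, susceptibility fully product-specific = p × (1+X/2)^−0.3. At 20%: 0.20 × 0.8765 = 17.5%. At 10%: 0.10 × 0.9443 = 9.4%.
- LY900014 counted, susceptibility fully shared: the same as Humalog.
- Half shared (simulation of 1,000,000 patients): about 13.1% Humalog against 15.3% LY900014 at 20%, and 8.1% against 8.8% at 10%.

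| True incidence, both insulins | Susceptibility | Counted gap | Patients in 42 |
|---|---|---|---|
| 20% | fully specific | 4.5 points | 1.9 |
| 20% | half shared | 2.2 points | 0.9 |
| 10% | fully specific | 1.4 points | 0.6 |
| 10% | half shared | 0.7 points | 0.3 |
| either | fully shared | 0 | 0 |

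**Step 3: a second model.** Take a constant hazard in a susceptible share of 30% to 100% of patients, with different LLTs for the two products, 10% true incidence on each, and 80% or 100% of recurrences at equal or lower severity. Humalog is counted at 8.2% to 9.6% and LY900014 at 10.0%. The gap is 0.4 to 1.8 points, or 0.2 to 0.8 patients in 42.

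**Step 4: a true excess on LY900014.** Suppose susceptibility is shared and LY900014 triples each patient's rate (shape 0.3, Humalog 20%).

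- True LY900014 incidence: 1 − (1 + 3 × 1.104)^−0.3 = 35.5%, an excess of 15.5 points.
- Counted LY900014: 0.8765 − (1 + 0.552 + 3.312)^−0.3 = 0.8765 − 0.6222 = 25.4%. Against 13.0% on Humalog, the counted excess is 12.4 points.
- In simulation with 42 patients, power of Prescott's test falls from about 56% to 43%.

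If the excess is instead independent of existing reactivity, it is nearly preserved: a true 4.5 points (10.0% against 14.6%) is counted as about 4.4.

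**Step 5: false positives.** With equal true incidence, Prescott rejection at alpha 0.10 is 3.3% unfiltered and 3.2% filtered (10%, half shared). In the worst case tried (20%, fully specific) it is 5.7% and 8.7%. Neither passes 10%.

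**The case against.** The strongest reply is that suppression is not certain. The limb on newly reported events can be read as counting any new onset in Period I or II, whatever happened earlier. The sentence on continuing events would also add little for the lead-in if every lead-in LLT already blocked later events. This stands as a competing reading. It does not remove the problem, because the maximum-severity sentence then no longer governs resolved terms and a programmer still has to choose.

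A reader might infer that the rule is a filter acting only through Humalog, so that LY900014 is made to look worse. The documents do not support that. The baseline also covers screening and preexisting conditions, when patients were on insulin lispro or aspart by pump, and a lead-in event blocks the same LLT on LY900014 as well. LY900014 is itself insulin lispro plus two excipients, given through the same pump and infusion sets, and the documents name no cause of reactions peculiar to Humalog. Bias against LY900014 needs product-specific susceptibility, which is an assumption.

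It is also fair to say that these comparisons serve an exploratory objective, that lead-in TEAEs are tabulated separately, and that the rule fits the protocol glossary's definition of a TEAE. Suppression is by LLT and severity, so a different term or a worse event still counts. These points limit the weight of the matter. They do not answer the undercount, or the loss of a true excess in Step 4.

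**Conclusion.** The point holds as an undercount on both insulins under the plain reading of Table ITSM.6.2 and 6.10.2, together with an ambiguity between two sentences of 6.10.2 that needs one governing rule. The direction of any effect on the comparison is open:

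- no bias if susceptibility is a patient trait shared by both insulins;
- a small bias against LY900014, about 0.3 to 2 patients in 42, if reactions are wholly or partly product-specific;
- attenuation of a true LY900014 excess if the new formulation amplifies reactions in already reactive patients.

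All sizes rest on assumed rates and mostly on a gamma shape of 0.3. No scenario tried raised the rejection rate above the nominal 0.10. SAEs, discontinuations due to AEs and the comparison of unplanned infusion set changes (SAP 6.10.7) do not depend on TEAE status and are untouched. This is a cheap improvement to the safety reporting, not a flaw that threatens the trial's conclusions.

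**What to change.** Keep the current TEAE definition for the main tables. For the systemic hypersensitivity and infusion site reaction comparisons (SAP 6.10.4.2 and 6.10.4.3), add a supplementary analysis that counts every event with a new onset date in Period I or II, with baseline severity set only by events ongoing at the first randomized dose. State in 6.10.2 how an event that resolved before randomization and then recurs is handled, so that the limb on newly reported events and the maximum-severity sentence give one answer.

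The cost is SAP wording, one derivation rule and a few extra tables. The rule on continuing events already requires knowing whether an event persisted, so new data should not be needed, though the documents do not list the AE form fields. The downside is that some unrelated recurrences will be counted, and those tables alone will depart from the convention of maximum severity per LLT.

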8.1. Discontinuation from Study Treatment

Patients who need to discontinue from study treatment will also be discontinued from the Study. Please refer to Section 8.2.

8.1.1. *Discontinuation of Inadvertently Enrolled Patients*

If the sponsor or investigator identifies a patient who did not meet enrollment criteria and was inadvertently enrolled, then the patient should be discontinued from study. If the investigator and the sponsor CRP/CRS agree that it is medically appropriate to continue, the investigator must obtain documented approval from the sponsor CRP/CRS to allow the inadvertently enrolled patient to continue in the study with IP. Safety follow-up is as outlined in Section 2 (Schedule of Activities), Section 9.2 (Adverse Events), and Section 9.4 (Safety) of the protocol.

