8.2. Discontinuation from the Study

Patients will be discontinued in the following circumstances:

- The investigator may decide that the patient should stop IP. If this decision is made because of an AE, SAE, or a clinically significant laboratory value, the study drug is discontinued for that patient and appropriate measures are to be taken. Lilly or its designee is to be alerted immediately
- The patient may decide to stop IP
- The patient becomes pregnant
- If an investigator, study site personnel performing assessments, or patient is unblinded, the patient must discontinue IP
- Frequent use of prohibited concomitant medication
- Use of pump other than the Medtronic MiniMed 670G.
- The patient has not used IP for more than 3 consecutive days
- Enrollment in any other clinical study involving an IP or enrollment in any other type of medical research judged not to be scientifically or medically compatible with this study
- Participation in the study needs to be stopped for medical, safety, regulatory, or other reasons consistent with applicable laws, regulations, and good clinical practice
- A patient experiences any episode of clinically diagnosed Diabetic Ketoacidosis (DKA) during the study
 - DKA is defined as an acute metabolic complication of diabetes characterized by hyperglycemia, hyperketonemia, and metabolic acidosis. Hyperglycemia causes an osmotic diuresis with significant fluid and electrolyte loss. DKA causes nausea, vomiting, and abdominal pain and can progress to cerebral

edema, coma, and death. DKA is diagnosed by detection of hyperketonemia and anion gap metabolic acidosis in the presence of hyperglycemia.

Treatment involves volume expansion, insulin replacement, and prevention of hypokalemia

- A patient participating in the pilot experiences any episode of severe hypoglycemia during the first 3 days of the pilot safety assessment
- A patient experiences >1 episode of severe hypoglycemia during the study
- A pilot patient's designated study companion does not comply with assigned responsibilities or is no longer available during pilot and transfer of study companion responsibilities is not possible for remainder of pilot safety assessment
- Investigator decision
 - the investigator decides that the patient should be discontinued from the study

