For continuous measures, summary statistics will include sample size, mean, SD, median, minimum, and maximum for both the actual and the change from baseline measurements. Least squares (LS) means and standard errors derived from the analysis models will also be displayed for the change from baseline measurements. Treatment comparisons will be displayed showing the treatment difference LS means and the 90% CIs for the treatment differences, along with the p-values for the treatment comparisons.

Unless otherwise specified, a restricted maximum likelihood based, mixed-effect model repeated measures (MMRM) analysis will be used to analyze continuous longitudinal variables. The longitudinal observations for both treatment periods will be included in the analysis. The model will include the fixed class effects of treatment, period, sequence, strata (HbA1c [$\leq 7.0\%$, $>7.0\%$] and percentage of time with SG values from 70 to 180 mg/dL over the 2 weeks prior to randomization [$\leq 75\%$, $>75\%$]), and the continuous, fixed covariate of baseline value. The

Kenward-Roger approximation will be used to estimate denominator degrees of freedom. An unstructured covariance structure will be used to model the within-patient errors. If this analysis fails to converge, a covariance structure of compound symmetry without heterogeneous variances will be used. If the model still does not converge, strata may be removed from the model. Significance tests will be based on LS means and Type III tests. SAS PROC MIXED will be used to perform the analysis.

For categorical measures (such as incidence of AEs), summary statistics will include sample size, frequency, and percentages. Prescott's exact test will be used for treatment comparisons, unless otherwise specified. Since Prescott's exact test is essentially a Fisher's exact test on the preference score and treatment sequence, if all events occurred in the same treatment sequence, p-values from Prescott's test will not be calculated.

For laboratory values, both conventional (CN) and Systeme International (SI) units will be presented. Therefore, both % and mmol/mol will be presented for HbA1c and both mg/dL and mmol/L will be presented for glucose measurements.

Table ITSM.6.2. Baseline and Post-Baseline Definitions and Patient Population by Study Period and Type of Analysis

Study Period/Analysis	Patient Population	Baseline Observations	Post-Baseline Observations
Lead-In Period (Overall^a only)			

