Rate of hypoglycemic events (per patient per year) 
 All Documented^b Nocturnal^b Non-Nocturnal (or Daytime) (Documented and between waking and bedtime)^b 	0-2, 0-4, 2-4 weeks	Wilcoxon signed-rank test
Incidence of hypoglycemic events 
 All Documented^b Nocturnal^b Non-Nocturnal (or Daytime)(Documented and between waking and bedtime)^b 	0-2, 0-4, 2-4 weeks	If there are ≥ 5 patients with at least one event within the specified time period, a generalized linear mixed model with options of the binomial distribution and logit link function with treatment, period, sequence. The within-patient error will be modeled as a compound symmetry without heterogeneous variance-covariance matrix. If the model does not converge or is not conducted due to the lower occurrence of events, Prescott's exact test will be used for analyses.
Endpoint	Analysis Period^a	Statistical Method
Rate of post-meal hypoglycemic events (per patient per year) 
 Documented^b 	$\leq 1, \leq 2, \leq 4, > 4$ and > 2 to ≤ 4 hours after start of a meal within 0-2, 0-4, and 2-4 weeks	Wilcoxon signed-rank test
Incidence of post-meal hypoglycemic events 
 Documented^b 	$\leq 1, \leq 2, \leq 4, > 4$ and > 2 to ≤ 4 hours after start of a meal within 0-2, 0-4, and 2-4 weeks	If there are ≥ 5 patients with at least one event within the specified time period, a generalized linear mixed model with options of the binomial distribution and logit link function with treatment, period, sequence. The within-patient error will be modeled as a compound symmetry without heterogeneous variance-covariance matrix. If the model does not converge or is not conducted due to the lower occurrence of events, Prescott's exact test will be used for analyses.
Rate of severe hypoglycemic events (per patient per year / 100 years)	0-2, 0-4, 2-4 weeks	Exposure adjusted rate per year / 100 years (calculated for each patient by total number of events divided by total exposure) will be provided and Wilcoxon signed-rank test will be used for treatment comparison.
Incidence of severe hypoglycemic events	0-2, 0-4, 2-4 weeks	Proportion of patients with severe hypoglycemia will be reported. The treatment comparison will be based on Prescott's exact test.

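### Prescott's exact test is planned for discontinuation due to an AE, but a patient who discontinues in Period I has no Period II outcome, and the SAP gives no rule for that case

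*SAP*

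**What the plan says.** - **Endpoint and test.** SAP 6.10.2: "The number and percentage of patients with SAEs and who discontinued from the study due to an AE will be summarized". The next sentence adds that "Prescott's exact test will be performed for treatment comparison".
- **Nature of the test.** SAP 6.1 explains that "Prescott's exact test is essentially a Fisher's exact test on the preference score and treatment sequence". It then adds a suppression rule: "if all events occurred in the same treatment sequence, p-values from Prescott's test will not be calculated".
- **Stopping treatment.** Protocol 8.1: "Patients who need to discontinue from study treatment will also be discontinued from the Study". SAP 6.10.1 restates this for unplanned stops.
- **Events that force withdrawal.** Protocol 8.2 lists any clinically diagnosed DKA, any severe hypoglycemia in a pilot patient during the first 3 days, and, for all patients, "A patient experiences >1 episode of severe hypoglycemia during the study".
- **Severe hypoglycemia.** In SAP Table ITSM.6.4 each patient's rate is events divided by exposure, and "Wilcoxon signed-rank test will be used for treatment comparison". Incidence is compared with Prescott's exact test.
- **Missing data.** SAP 6.3 deals only with continuous variables, through the MMRM.
- **Population.** SAP 6.1 and Table ITSM.6.3 place these analyses on the Randomized Population, using all data regardless of IP use. Completing both periods is not required.

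**The concern.** A preference score compares a patient's Period I outcome with the same patient's Period II outcome. For most adverse events both outcomes usually exist. For discontinuation due to an AE they cannot both exist when the event is in Period I, because the event itself removes the second period. The endpoint and the test therefore do not fit each other, and this holds for every Period I event of this type.

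The programmer must then choose between dropping these patients and crediting them with an event-free period on a treatment they never received. The SAP does not make that choice. At stake is whether a reported p-value for tolerability reflects the data or an unstated convention, and in some cases whether any p-value is reported at all.

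The paired severe hypoglycemia rate (endpoint 5) has a related gap. A patient withdrawn in Period I has no Period II exposure, so the Period II rate is undefined and there is no paired difference.

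**Working it through.** **The plan's own figures.** The documents give no figure for the Prescott tests. The sample size reproduces: 5/(10/√36) = 3.0, and Φ(3.0 − 1.645) = 0.912 (0.90 with the noncentral t), against about 90% stated. For dropout, 36/0.88 = 40.9, so 41 against 42 stated, which is close enough.

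**How much could be lost.** All-cause dropout of 12% is 42 × 0.12 = 5.0 patients. If the risk is equal in each period (assumption), the per-period risk is 1 − √0.88 = 0.062. That gives 42 × 0.062 = 2.6 dropouts in Period I and 42 × 0.938 × 0.062 = 2.4 in Period II. If all were AE discontinuations, which is an upper bound, a complete-pairs test would lose about half of the events.

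**Inputs for the illustrations.** 21 patients per sequence (SAP 5.2) and two-sided 0.10 (SAP 6.1). The event counts are assumptions, because the documents give no expected rate of AE discontinuation. Score = Period I event minus Period II event.

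**Illustration A.** LY900014 discontinuations: 3 in Period I (Sequence A) and 2 in Period II (Sequence B). None on Humalog.

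| Handling | Data compared | p | Reported under SAP 6.1? |
|---|---|---|---|
| Complete pairs | 2/21 (Seq. B) vs 0/18 (Seq. A) | C(21,2)/C(39,2) + C(18,2)/C(39,2) = 0.283 + 0.206 = 0.49 | No; both events are in Sequence B |
| Absent period scored no event, ordered score | Seq. A: 3 at +1, 18 at 0; Seq. B: 19 at 0, 2 at −1 | 0.066 | Yes |
| Same table, unordered (Freeman-Halton) | as above | 0.11 | Yes |
| Exact test stratified by period | Period I 3/21 vs 0/21; Period II 2/21 vs 0/18 | 0.057 | Not a Prescott test |

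For the last row, the probability that all five events fall on LY900014 is [C(21,3)/C(42,3)] × [C(21,2)/C(39,2)] = 0.1159 × 0.2834 = 0.0328. The opposite extreme, all five on Humalog, has probability 0.0239. The sum is 0.057.

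**Illustration B.** Five LY900014 discontinuations in Period I and none elsewhere. On complete pairs every score is zero, so there is nothing to test. With no-event scoring, all five events are in Sequence A and SAP 6.1 withholds the p-value. Fisher's exact test on Period I, 5/21 vs 0/21, gives 2 × C(21,5)/C(42,5) = 2 × 20,349/850,668 = 0.048.

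**Direction.** Suppose three Humalog discontinuations in Period I and three LY900014 discontinuations in Period II, all in Sequence B. Complete pairs give 3/18 vs 0/21, p = 0.089 against LY900014. SAP 6.1 would withhold this p-value too, but it shows the direction. The period-stratified test has three events on each treatment and gives p = 1.0. Here dropping Period I events creates an apparent difference.

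**Severe hypoglycemia and SAEs.** Outside the 3-day pilot, one severe episode does not end participation, and an SAE does not by itself require withdrawal. Those patients continue and can supply both periods. The gap covers only patients whose participation ends in Period I, for example through DKA, a severe episode in the pilot, or more than one severe episode.

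**The case against.** The strongest reply is that the SAP never limits Prescott's test to complete pairs. Its population is all randomized patients, and AE discontinuation is listed for the full 0 to 8 weeks regardless of IP use. Scoring an absent period as no event fits that text and lets the patients in. On the ordered score it gives 0.066, close to the stratified 0.057. This stands: a reader might infer that Period I discontinuations cannot enter the test, but the documents leave the handling open. It does not answer the suppression rule, nor the crediting of an insulin never received.

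Other stronger readings also fail:

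- A reader might infer bias toward no difference. The third example shows that the loss can go either way.
- A reader might extend the full loss to all SAEs and severe hypoglycemia. Protocol 8.2 supports this only for patients whose participation ends in Period I.
- A reader might conclude that the harm is hidden. It is not: SAP 6.10.2 counts Period I and Period II AE discontinuations by treatment and lists them, SAEs and severe hypoglycemia are listed, and narratives cover SAEs and AE discontinuations. The gap concerns the p-values and, for severe hypoglycemia, the paired rate comparison.

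It is also fair to say that the illustration counts are invented, that 12% is all-cause dropout, and that in Illustration B the suppression rule alone would remove the p-value even if the patients were scored.

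**Conclusion.** The concern holds in a limited form. For discontinuation due to an AE, the planned test needs a second-period outcome that no Period I discontinuer has, and no missing-data rule covers binary or paired tests. On complete pairs all Period I discontinuations are lost. With no-event scoring they enter, but the p-value is still withheld when all events fall in one sequence, as happens when every event occurs on one treatment in Period I.

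Under the assumed counts, the same data give 0.49 (withheld), 0.066, 0.11 or 0.057 against a level of 0.10, and the Period-I-only case gives no Prescott p-value against a Fisher p of 0.048. These values rest on 21 patients per sequence and on hypothetical event counts. They show sensitivity to an unstated choice and do not predict results. The extension to SAEs and severe hypoglycemia is partial. The change should be made because it is cheap and the mismatch for AE discontinuation is structural.

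**What to change.** 1. In SAP 6.10.2, replace Prescott's test for discontinuation due to an AE with an exact test stratified by period. The risk set in each period is the patients who received at least 1 dose of that period's IP. Each patient can discontinue only once, so the period-wise risk sets are valid. State that the no-p-value rule in SAP 6.1 does not apply to this test.
2. For SAEs and severe hypoglycemia, keep the paired tests. State how one-period patients are handled in Prescott's test and in the Wilcoxon signed-rank test, and report how many patients with an event were left out of each.
3. Add a supportive Fisher's exact test on Period I by assigned treatment for SAEs and for severe hypoglycemia incidence. It keeps everyone who withdrew in that period.

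The cost is SAP wording and minor programming. The Period I test has lower power than the full crossover comparison for events that do not cause withdrawal, so it supplements the paired tests and does not replace them.
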